15.2.1 Sample Size Calculations for Immunogenicity

A power analysis was performed using the paired t-test for over time differences (i.e., measures at Baseline vs. Day 1, Day 57) to test the first hypotheses that neoantigen DNA vaccines can induce and/or enhance neoantigen-specific T cell responses (e.g., the frequency of neoantigen-specific CD8 T cells in ELISPOT and multi-parameter flow cytometry). Assuming a moderate correlation between measures taken from the same individual, the designed sample size (n=24 patients) allows us 80% power at 1-sided 0.05 alpha level to detect a minimum of $0.5 \times SD$ for overtime changes. A power analysis was also performed using the 2-sample t-test for between-arm differences (i.e., measures at Day 113, Day 169) to test the second hypotheses that durvalumab will enhance the response to neoantigen DNA vaccines. We expect that the majority of the patients enrolled will remain in the study and lead to at least 10 evaluable patients/arm for such comparison. The designed sample size (n=10 patients/arm) provides us 80% power at 1-sided 0.05 alpha level to detect a minimum of $1.2 \times SD$ for between-group differences. Preliminary data from our phase 1 trial for mammaglobin-A DNA vaccine, though on patients with stable metastatic breast cancer and targeting a tissue-specific antigen, showed that the frequency of antigen-specific CD8 T cells can be measured with ~20% coefficient of variation ($CV=SD/Mean$). Therefore, the designed sample size allows us to detect ~10% for over-time differences and ~15% for between-group differences respectively. As a study to estimate preliminary information, we expect that ~20% difference will provide an adequate signal for immunogenicity. In addition, we anticipate that more power could be achieved because the actual data analysis will be performed using mixed model which uses data more efficiently and allows us to borrow information across multiple time points.

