15.3.2 Immune response

Neoantigen-specific T cell response to neoantigen DNA vaccines + durvalumab is the secondary objective of the trial. Neoantigen specific T cell responses will be measured by Luminex, ELISPOT, multiparametric flow cytometry, and CyTOF. The frequency of antigen-specific CD8 T cells in each arm at each time will be summarized using means, standard deviations and medians. The change over time as well as the difference between arms will also be compared using linear mixed model for repeated measurement data. The immunogenicity of the neoantigen DNA vaccine will also be analyzed qualitatively by summarizing the phenotypic and functional characteristics of epitope-specific CD8 T cells. Responses will be considered positive if the number of T cells after vaccination is greater than two standard deviations above the mean before vaccination [101]. The frequency of positive responses at each time point will be assessed and binomial response rates with 95% confidence interval estimates will be presented. In addition to presenting the binomial response rates, graphical and tabular summaries of the underlying distributions will be made.

To determine whether the observed difference is larger than might be expected by chance, a permutation test will be used to compare the observed test statistic to the distribution of test statistics that would be seen if there were no difference between the two arms. Specifically, we will randomly shuffle the data and calculate the test statistic from the shuffled data. This procedure will be repeated 10,000 times and the resultant testing statistics will provide an accurate representation of the null distribution. The observed test statistics of between-arm differences will be compared to the null distributions. For each outcome, the permuted p-value will be the fraction of permuted samples that resulted in a small statistic than the original sample [103].

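### The permutation p-value in section 15.3.2 counts the wrong tail for the natural between-arm statistics, and the plan names neither the statistic nor its sign

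*Combined protocol and SAP*

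**What the plan says.** Section 15.3.2 introduces the between-arm permutation test with its aim: "To determine whether the observed difference is larger than might be expected by chance, a permutation test will be used". The data are shuffled and the statistic recalculated: "This procedure will be repeated 10,000 times". Then "The observed test statistics of between-arm differences will be compared to the null distributions", and for each outcome "the permuted p-value will be the fraction of permuted samples that resulted in a small statistic than the original sample". The form of the statistic, the direction of subtraction and the sidedness are not given.

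The direction of interest is in section 15.2.1. The between-arm power analysis was done "to test the second hypotheses that durvalumab will enhance the response to neoantigen DNA vaccines". It expects "at least 10 evaluable patients/arm for such comparison" and says that this number "provides us 80% power at 1-sided 0.05 alpha level to detect a minimum of" 1.2 SD, using a two-sample t-test.

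**The concern.** A permutation p-value should count the permuted statistics at least as extreme as the observed one in the direction of the alternative. The alternative here is that the combination arm responds more strongly. For combination minus vaccine, or for an unsigned statistic such as |t| or F, stronger evidence means a larger value, so the upper tail is needed. The written rule counts the smaller values.

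Under the signed form, a benefit would look null and a detriment would be declared significant. Under the unsigned form, both would be missed. This rule decides whether the difference exceeds chance for each immune outcome. Two analysts following the text in good faith could report p = 0.008 or p = 0.992 from the same data. Choosing the statistic or tail after seeing the results would forfeit prespecification.

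**Working it through.** **Inputs.** From section 15.2.1: 10 evaluable patients per arm, one-sided alpha 0.05, difference 1.2 SD, two-sample t-test. From section 15.3.2: 10,000 permutations and the lower-tail rule. Assumptions: normal outcomes, one value per patient, arms exchangeable under no effect.

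**1. The plan's own figure.** Degrees of freedom are 2 × 10 − 2 = 18. The noncentrality is 1.2 × √(10/2) = 2.683. The one-sided critical value is t(0.95; 18) = 1.734. Power is P(T > 1.734 | ncp 2.683) = 82.5%. The smallest difference detectable with 80% power is 1.156 SD, which rounds to 1.2, and 10 per arm is the smallest size giving at least 80% power at 1.2 SD. A two-sided test would need 1.32 SD. The plan's figure is therefore reproduced, and it is one-sided.

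**2. p-value at an observed difference of exactly 1.2 SD.** Here t = 2.683. The one-sided upper-tail p is 0.0076 and the two-sided p is 0.0152. The fraction of smaller values is 1 − 0.0076 = 0.9924 for the signed statistic and 1 − 0.0152 = 0.9848 for |t|. Permutation on 200 simulated data sets scaled to this difference, with 10,000 permutations each, gave these means:

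| Statistic | Fraction smaller (as written) | (1 + count ≥ observed)/10,001 |
|---|---|---|
| combination − vaccine | 0.9923 | 0.0078 |
| \|t\| | 0.9846 | 0.0155 |
| vaccine − combination | 0.0077 | not applicable: the written tail is already right |

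**3. Rejection rate at 0.05, true benefit of 1.2 SD.**

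- Signed, as written: P(T < −1.734 | ncp 2.683) = 1.2 × 10⁻⁵, about 0.001%. Upper tail: 82.5%.
- |t|, as written: rejection requires |t| below its 5th percentile under no effect, t(0.525; 18) = 0.064. P(|T| < 0.064 | ncp 2.683) = 0.14%. Upper tail, two-sided: 71.8%.

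**4. Check by permutation** (4,000 simulated trials per scenario, 1,999 shuffles each).

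| True effect | Signed, as written | Signed, upper tail | \|t\|, as written | \|t\|, upper tail |
|---|---|---|---|---|
| +1.2 SD | 0.0% | 83.1% | 0.1% | 72.4% |
| 0 | 4.8% | 5.0% | 5.3% | 4.6% |
| −1.2 SD | 82.8% | 0.0% | 0.1% | 71.4% |

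With no effect, all four rules reject about 5%, so a check of the type I error alone would not reveal the fault.

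**The case against.** The strongest reply is that a reversed analysis is not shown. The sentence is ungrammatical, so 'smaller' is an inference, and the paragraph's opening makes the intended direction plain. The sentence also cites a work (reference 103) whose title concerns resampling-based p-value adjustment. If the resampled quantity is itself a p-value, smaller is the correct tail. That possibility is real, as is a vaccine-minus-combination statistic. But the plan states neither, and it speaks of test statistics of between-arm differences. Calling the sentence a slip concedes that an operative rule needs correcting.

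It is also fair that the damage is contained. A linear mixed model compares the arms as well, the objective is secondary, and the primary safety analysis is descriptive. A p-value near 0.99 beside a positive contrast would probably be noticed, and apart from ties it could be recovered as one minus the printed value. This limits the severity but does not justify leaving the rule as it is.

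The 5% rate under no effect assumes exchangeable arms. Sections 8.2 and 8.3 replace combination patients without a T cell response, with no matching rule for the vaccine-only arm. If those patients are left out of the comparison, even the corrected test can reject too often. With assumed response rates of 70% to 90% and correlations of 0.3 to 0.7 between early and later response, it rejects about 6% to 20% under no effect; the documents give neither quantity. This qualifies the null figures above. It is a separate bias and does not change which tail is right.

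**Conclusion.** The concern holds. As written, the p-value rule is the wrong tail for a combination-minus-vaccine statistic and for an unsigned one. It is right only if the statistic is vaccine minus combination, is a p-value, or otherwise gets smaller as benefit grows. The plan specifies none of these.

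At the effect the trial was sized for, the chance of supporting the durvalumab hypothesis falls from 82.5% to about 0.001% (signed), or from 71.8% to 0.14% (|t|). Under the signed form, a true detriment of 1.2 SD would be declared significant about 82% of the time. With exchangeable arms the fault is lost power in the intended direction, not an inflated false-positive rate.

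The exact percentages rest on normal data with one value per patient; the tail reversal does not. This should be fixed, but the consequence is confined to the secondary immune-response objective.

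**What to change.** In section 15.3.2, name the statistic and its sign, for example the mixed-model combination-minus-vaccine contrast divided by its standard error. State the sidedness. For the one-sided test of section 15.2.1, define p = (1 + number of permuted statistics ≥ observed)/(10,000 + 1); for a two-sided test, apply the same formula to absolute values. If a p-value was meant as the resampled statistic, say so and keep the lower tail. Adding 1 to numerator and denominator is a refinement that changes p by at most 0.0001.

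In the same edit, state that shuffling permutes arm labels across whole patients, keeps each patient's time series together and holds the analysed arm sizes fixed. This is a clarification, not the correction of a shown error.

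The change takes one or two sentences, plus the shuffling clarification, and costs nothing in data, patients or time. It should be made before between-arm results are seen.

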16 DATA MANAGEMENT

Case report forms with appropriate source documentation will be completed according to the schedule below.

Case Report Form	Submission Schedule
Original Consent Form	Prior to registration
Demographics Form On-Study Form	Prior to starting treatment
Physical Exam Form	Baseline Day 1 Day 29 Day 57 Day 85 Day 113 Day 141
Durvalumab Form	Day 85 Day 113 Day 141 Day 169
Randomization Form	After end of SOC adjuvant therapy
Vaccine Administration Form	Day 1 Day 29 Day 57 Day 85 Day 113 Day 141
Immune Monitoring Form	Baseline End of SOC adjuvant therapy Day 1 Day 57 Day 113 Day 169 Week 52 after completion of neoantigen DNA vaccine therapy
Imaging Form	Baseline
Toxicity Form Concomitant Medications Form	Continuous
Follow Up Form	Week 52 after completion of neoantigen DNA vaccine therapy Year 2 Year 3 Year 4 Year 5
MedWatch Form	See Section 13.0 for reporting requirements

16.1 Adverse Event Collection in the Case Report Forms

All adverse events that occur beginning with start of treatment (minus exceptions defined in Section 13) must be captured in the Toxicity Form. Baseline AEs should be captured on the Medical History Form.

Participant death due to disease progression should be reported on the Toxicity Form as grade 5 disease progression. If death is due to an AE (e.g. cardiac disorders: cardiac arrest), report as a grade 5 event under that AE. Participant death must also be recorded on the Death Form.

17 REGULATORY AND ETHICAL OBLIGATIONS

17.1 Informed consent

In accordance with US FDA regulations (21 CFR 50) and guidelines (Federal Register, May 9, 1997, Vol. 62, Number 90 - ICH Good Clinical Practice Consolidated Guideline) it is the investigator's responsibility to ensure that informed consent is obtained from the subject before participating in an investigational study, after an adequate explanation of the purpose, methods, risks, potential benefits and subject responsibilities of the study. Procedures that are to be performed as part of the practice of medicine and which would be done whether or not study entry was contemplated, such as for diagnosis or treatment of a disease or medical condition, may be performed and the results subsequently used for determining study eligibility without first obtaining consent. On the other hand, informed consent must be obtained prior to initiation of any screening procedures that are performed solely for the purpose of determining eligibility for research.

Each subject must be given a copy of the informed consent. The original signed consent must be retained in the institution's records and is subject to review by the sponsor, the HRPO and any other applicable regulatory agencies responsible for the conduct of the institution. All elements listed in the ICH Good Clinical Practice guidelines must be included in the informed consent.

Informed consent will be obtained by either the principal investigator or by individuals approved by the principal investigator. Informed consent will be obtained from the subject after the details of the protocol have been reviewed. The individual responsible for obtaining consent will assure, prior to signing of the informed consent, that the subject has had all questions regarding therapy and the protocol answered.

17.2 Institutional Review Board

In accordance with US FDA regulations (21 CFR 56) and guidelines (Federal Register, May 9, 1997 Vol. 62 Number 90 - ICH Good Clinical Practice Consolidated Guideline) all research involving human subjects must be reviewed and approved by the local IRB. All modifications to the protocol, consent forms, or other study documents must be reviewed and approved by the local IRB. At Washington University School of Medicine, the Human Research Protection Office serves as the local IRB.

17.3 Subject confidentiality

In order to ensure subject confidentiality, each subject will be assigned a study number. Subject samples and medical information will be de-identified and labeled with the study number. The link between subject identification and study number will be safeguarded in a secure file in a locked room, and access will be restricted to the principal investigator, study coordinator, and other co-investigators as necessary.

Collected data will be recorded on case report forms. Case report forms will be safeguarded in a locked cabinet and/or a password-protected secure computer drive and access will be restricted to the principal investigator, study coordinator, and other co-investigators as necessary. Subject medical information related to, or obtained for the purposes of this trial are confidential, and disclosure to third parties is prohibited. The exception is regulatory authorities including the FDA, NIH/OBA, and the local IRB. Data from this study must be available for inspection on request of regulatory authorities including the FDA and the local IRB.

18 ADMINISTRATIVE AND LEGAL OBLIGATIONS

18.1 Study documentation and retention of records

18.1.1 Study documentation

Source documents are original documents, data, and records from which the subject's data are obtained. These include but are not limited to hospital records, clinical and office charts, laboratory and pharmacy records, diaries, diagnostic imaging studies, and correspondence.

The principal investigator and staff are responsible for maintaining a comprehensive file of all study-related documents, suitable for inspection at any time by representatives from the PRMC, HRPO, FDA, and any other applicable regulatory agency.

Pertinent documents in the study file include:

- (1) The original protocol with all amendments
- (2) Curriculum vitae of principal investigator and co-investigators
- (3) Approval notification and any other correspondence with the PRMC, HRPO, NIH RAC and FDA

Pertinent documents in each individual subject file include:

- (1) Informed consent forms
- (2) Case report forms
- (3) Supporting copies of source documentation

All original source documentation must be readily available.

18.1.2 Retention of records

The principal investigator must retain records related to this study including protocols; amendments; IRB/IBC approvals; FDA IND records and other correspondence; completed, signed and dated consent forms; patient medical records; case report forms; drug accountability records and any other correspondence related to the conduct of the study.

U.S. FDA regulations (21 CFR 312.62[c]) require that all records pertaining to the conduct of this study, must be retained by the responsible investigator for a minimum of 2 years after marketing application approval. If no application is filed, these records must be kept 3 years after the investigation is discontinued and the U.S. FDA and the applicable local health authorities are notified.

18.2 Policy regarding research-related injuries

Washington University School of Medicine investigators and their staffs will try to reduce, control, and treat any complications from this research.

Any subjects who believe that they have been injured as a result of participation in this study will be instructed to contact the principal investigator, [name]. at [contact]. Alternatively, they can contact the Human Research Protection Office, at [contact].

Decisions about payment for medical treatment for research-related injuries will be made by Washington University School of Medicine.

In general, Washington University School of Medicine will provide no long-term medical care or financial compensation for research-related injuries.

18.3 Study termination

The principal investigator and the Siteman Cancer Center reserve the right to terminate the study. The principal investigator will notify the PRMC and HRPO in writing of the study's completion or early termination.

20 APPENDICES

20.1 Abbreviations

AE	Adverse Event
CBER	Center for Biologics Evaluation and Research
CFR	Code of Federal Regulations
CPA	Cooperative Project Assurance
CR	Complete response
CRA	Clinical Research Associate
CRF	Case Report Form
CT	Computed Tomography
CTCAE	Common Terminology Criteria for Adverse Events
CTEP	Cancer Therapy Evaluation Program
DNA	Deoxyribonucleic acid
DCTD	Division of Cancer Treatment and Diagnosis
ELISPOT	Enzyme-linked immunospot assay
ECOG	Eastern Cooperative Oncology Group
FDA	Food and Drug Administration
FWA	Federal-wide Assurance
GLP	Good Laboratory Practice
GMP	Good Manufacturing Practice
GPC	Gel permeation chromatography
HIPAA	Health Insurance Portability and Accountability Act
HLA	Human leukocyte antigen
HRPO	Human Research Protection Office (Institutional Review Board at WUSM)
IBC	Institutional Biosafety Committee
ICH	International Conference of Harmonization
IDB	Investigational Drug Branch
IRB	Institutional Review Board
LD	Longest diameter
MPA	Multiple Project Assurance
MRI	Magnetic Resonance Imaging
NCI	National Cancer Institute
NIH	National Institutes of Health
OBA	Office of Biotechnology Activities
OHRP	Office for Human Research Protection
PBMC	Peripheral blood mononuclear cell
PD	Progressive disease
PHI	Protected Health Information
PR	Partial response
RAC	Recombinant DNA Advisory Committee
RECIST	Response Evaluation Criteria in Solid Tumors
QASMC	Quality Assurance and Safety Monitoring Committee
SAE	Serious Adverse Event
SAS	Statistical Analysis System; Analytical software from the SAS Institute, Cary, NC
SCC	Siteman Cancer Center
SCIP	Siteman Cancer Information Portal
SD	Stable disease
SD	Standard Deviation
THF	Tetrahydrofuran
UPN	Universal Product Number
WUSM	Washington University School of Medicine
WUSTL	Washington University in Saint Louis

20.2 ECOG/Zubrod performance status scale

ECOG/Zubrod Score	Performance Status
0	Asymptomatic
1	Symptomatic, fully ambulatory
2	Symptomatic, in bed < 50% of the day
3	Symptomatic, in bed > 50% of the day but not bedridden
4	Bedridden
5	Dead

20.3 National Cancer Institute Common Terminology Criteria for Adverse Events

This study will collect adverse events using the NCI Common Terminology Criteria for Adverse Events v4.03 (CTCAE), if applicable. The CTCAE provides a descriptive terminology that is to be used for adverse event reporting. A grading (severity) scale is also provided in the CTCAE for each adverse event term. An electronic version of the CTCAE may be accessed through the web at <http://ctep.cancer.gov>. Alternatively, a full copy is available from the principal investigator.

20.4 Definitions for Adverse Event Reporting

A. Adverse Events (AEs)

As defined in 21 CFR 312.32:

Definition: any untoward medical occurrence associated with the use of a drug in humans, whether or not considered drug-related.

Grading: the descriptions and grading scales found in the revised NCI Common Terminology Criteria for Adverse Events (CTCAE) version 5.0 will be utilized for all toxicity reporting. A copy of the CTCAE version 5.0 can be downloaded from the CTEP website.

Attribution (relatedness), Expectedness, and Seriousness: the definitions for the terms listed that should be used are those provided by the Department of Health and Human Services' Office for Human Research Protections (OHRP). A copy of this guidance can be found on OHRP's website: <http://www.hhs.gov/ohrp/policy/advevntguid.html>

B. Suspected Adverse Reaction (SAR)

As defined in 21 CFR 312.32:

Definition: any adverse event for which there is a reasonable possibility that the drug caused the adverse event. "Reasonable possibility" means there is evidence to suggest a causal relationship between the drug and the adverse event. "Suspected adverse reaction" implies a lesser degree of certainty about causality than adverse reaction, which means any adverse event caused by a drug.

C. Life-Threatening Adverse Event / Life Threatening Suspected Adverse Reaction

As defined in 21 CFR 312.32:

Definition: any adverse drug event or suspected adverse reaction is considered "life-threatening" if, in the view of the investigator, its occurrence places the patient at immediate risk of death. It does not

include an adverse event or suspected adverse reaction that, had it occurred in a more severe form, might have caused death.

D. Serious Adverse Event (SAE) or Serious Suspected Adverse Reaction

As defined in 21 CFR 312.32:

Definition: an adverse event or suspected adverse reaction is considered “serious” if, in the view of the investigator, it results in any of the following outcomes:

- Death
- A life-threatening adverse event
- Inpatient hospitalization or prolongation of existing hospitalization
- A persistent or significant incapacity or substantial disruption of the ability to conduct normal life functions
- A congenital anomaly/birth defect
- Any other important medical event that does not fit the criteria above but, based upon appropriate medical judgment, may jeopardize the subject and may require medical or surgical intervention to prevent one of the outcomes listed above

E. Protocol Exceptions

Definition: A planned change in the conduct of the research for one participant.

F. Deviation

Definition: Any alteration or modification to the IRB-approved research without prospective IRB approval. The term “research” encompasses all IRB-approved materials and documents including the detailed protocol, IRB application, consent form, recruitment materials, questionnaires/data collection forms, and any other information relating to the research study.

A minor or administrative deviation is one that does not have the potential to negatively impact the rights, safety, or welfare of participants or others or the scientific validity of the study.

A major deviation is one that does have the potential to negatively impact the rights, safety, or welfare of participants or others or the scientific validity of the study.

